### 7.3.2.3. Confirmed ORR and Confirmed BOR by mRECIST v1.1

Under mRECIST v1.1, if radiologic imaging shows CR or PR, a tumor assessment should be repeated at a minimum of 4 weeks to confirm the response in order to claim the CR or PR as the confirmed BOR. If there is no second CR or PR tumor assessment, the CR or PR will be unconfirmed. Table 4 lists the scenarios that can occur after an unconfirmed CR or PR in and provides a rule for determining the confirmed BOR in each scenario. A sensitivity analysis for the ORR assessed under mRECIST v1.1, in which BOR is determined using unconfirmed PR and CR, is detailed in Section 7.3.2.4.

The mRECIST v1.1 instrument was adapted from RECIST v1.1 to include criteria that accounts for new lesions that can occur in immuno-oncology subjects before the occurrence of an SD, PR, or CR. Under mRECIST v1.1, if radiologic imaging shows PD, tumor assessment should be repeated at a minimum of 4 weeks but not more than 6 weeks later to confirm the progression. If there is no second PD tumor assessment in the 4- to 6-week follow-up time, the PD will be defined as unconfirmed. Table 6 lists the scenarios that can occur after an unconfirmed PD in at least 4 weeks and no more than 6 weeks and provides rules for determining whether or not the unconfirmed PD will be counted as an event in the corresponding scenario.

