As noted above, if disease progression is observed, the study site may elect to continue treatment, repeat imaging at a minimum of 4 weeks, but no later than 6 weeks later, and assess tumor response or confirmed progression per mRECIST.

In determining whether or not the tumor burden has increased or decreased, study site investigators should consider all target lesions as well as nontarget lesions. Subjects who are deemed clinically unstable are not required to have repeat tumor imaging for confirmation. If radiologic progression is confirmed by subsequent scan, then the subject should be discontinued from study treatment. If radiologic progression is not confirmed, then the subject should resume or continue study treatment and have the next tumor imaging according to the Protocol schedule (see Table 10). If progression is not confirmed and the subject continues on treatment, then the next scan that documents disease progression (and is confirmed by a second scan at least 4 weeks, but no later than 6 weeks later) will be considered the date of disease progression.

If a subject has confirmed radiographic progression (ie, 2 scans at least 4 weeks, but no later than 6 weeks, apart demonstrating progression) per mRECIST, but the subject is achieving a clinically meaningful benefit, an exception to continue treatment may be considered after consultation with the medical monitor. Clinically stable subjects at the confirmatory scan should also have no further increase in the target lesions, no unequivocal increase in nontarget lesions, and no additional new lesions develop (nonworsening disease progression) to continue study treatment.

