**Table 6: Rules for Determining PD Event Status After an Unconfirmed PD Under mRECIST v1.1**

Event Occurring After Unconfirmed PD in the Confirmation Window (4-6 weeks)	PD Event Status
Subject had end of study/end of treatment or started new anticancer therapy.	PD will be confirmed as a PD.
Subject had a confirmed PD.	PD will be confirmed as a PD.
Subject had a CR, PR, SD, or NE.	PD will not be considered as a PD and counted as corresponding CR, PR, SD, or NE for the second timepoint only.

Confirmed ORR by mRECIST v1.1 will be summarized by treatment group and tumor type for the Phase 2 response evaluable population.

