#### **7.3.2.4. Unconfirmed ORR and Unconfirmed BOR by mRECIST v1.1 – Sensitivity and Supportive Analyses for Confirmed ORR and Confirmed BOR by mRECIST v1.1**

A sensitivity analysis for the ORR assessed under mRECIST v1.1 will be performed using unconfirmed CRs and PRs. The unconfirmed BOR is defined as the best response recorded postbaseline prior to and including the first PD, in the order of CR, PR, SD, PD and NE. For this definition, responses of CR and PR do not need to be confirmed at a subsequent timepoint. In the case of SD, measurements must meet the SD criteria at least once after the date of first dose at a minimum interval of 49 (56 – 7) days. Subjects who fail to meet this criterion will have confirmed BOR of PD if the next available assessment indicates PD or NE if there is no additional assessment available.

Unconfirmed ORR as assessed by mRECIST v1.1 will be summarized by treatment group and dose level for the Phase 1 response evaluable population and by treatment group and tumor type for the Phase 2 response evaluable population.

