**7.3.7.2. Progression-Free Survival by mRECIST v1.1**

Under mRECIST v1.1, PFS is defined as the length of time between the baseline visit (Day 1) and the earlier of death or first confirmed assessment of PD (as described in Section [7.3.2.3 Table 6](#)).

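### Read literally, SAP Table 6 does not count the mRECIST progression of subjects who stop before week 4, and SAP 7.3.2.4 ends unconfirmed mRECIST response at the first PD

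*SAP*

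**What the plan says.** **Confirmation rule.** SAP 7.3.2.3 says that after a first PD under mRECIST, "tumor assessment should be repeated at a minimum of 4 weeks but not more than 6 weeks later to confirm the progression". It continues: "If there is no second PD tumor assessment in the 4- to 6-week follow-up time, the PD will be defined as unconfirmed". That label is not final, because Table 6 "provides rules for determining whether or not the unconfirmed PD will be counted as an event in the corresponding scenario".

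**Table 6.** Its left column is headed "Event Occurring After Unconfirmed PD in the Confirmation Window (4-6 weeks"), and the sentence introducing the table repeats the same limits.
- Row 1 counts the PD if: "Subject had end of study/end of treatment or started new anticancer therapy".
- Row 2 counts it if PD is confirmed.
- Row 3 cancels it if the later status is CR, PR, SD or NE.

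**Endpoints that use it.** mRECIST PFS (SAP 7.3.7.2) ends at death or the "first confirmed assessment of PD". mRECIST DOR (7.3.3.2) uses the same event, and duration of disease control (7.3.4) refers back to 7.3.2.3.

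**Protocol conduct.** Protocol Table 13 has clinically unstable subjects discontinue at the first radiologic PD, with repeat imaging left to the physician. Protocol 7.7.1 adds: "Subjects who are deemed clinically unstable are not required to have repeat tumor imaging for confirmation". Protocol 7.7.1.1.2 and SAP 9.1.2.1 ask for confirmation of progression only in clinically stable subjects.

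**Unconfirmed mRECIST response.** SAP 7.3.2.4 states: "The unconfirmed BOR is defined as the best response recorded postbaseline prior to and including the first PD".

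**The concern.** The stopping events in Table 6 row 1 appear meant to count progression in subjects who stop without a second scan. Yet the column heading asks for those events in weeks 4-6, and the subjects most likely to stop without a scan stop earlier. If a programmer follows the heading, these PDs stay unconfirmed and are not events. Their follow-up is then censored at the PD scan or runs on to death. Such censoring is informative, because these subjects are stopping for clinical deterioration. Two programmers could also produce different mRECIST PFS from the same data.

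The second problem is that 7.3.2.4 uses nearly the same cut-off sentence as the RECIST v1.1 section (7.3.2.2). mRECIST exists to allow a response after an early, unconfirmed PD. A cut-off at the first PD, taken literally, excludes exactly those responses.

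**Working it through.** **1. Which PDs have no row.** The end-of-treatment visit is set within 3 days of withdrawal (Protocol synopsis), so an immediate stop at the first PD falls before week 4.

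| After the first PD | Row that expressly applies |
|---|---|
| Second PD scan at weeks 4-6 | Row 2: counted |
| End of treatment, end of study or new therapy at weeks 4-6 | Row 1: counted |
| CR, PR, SD or NE at weeks 4-6 | Row 3: cancelled |
| Treatment ended before week 4, no scan | None |
| Still on treatment, no scan in the window | None |
| Next PD scan after week 6 | None |

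**2. What happens to an uncounted PD.** SAP Table 7 censors a subject without progression at the last valid scan, which here is the PD scan itself. A later death is an event unless it follows more than one missed assessment, when Table 7 censors it.

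**3. Size.** The documents give no median, event count or affected share for mRECIST PFS, so there is no stated figure to reproduce. The following is an illustration on assumed inputs.
- Time to PD: exponential, true median 2.5, 4 or 6 months (assumed), at 4.345 weeks per month.
- PD scan: the next 8-weekly scan, 8 × ceiling(T/8) weeks, plus or minus up to 1 week (interval from Protocol 7.7.1.1.2).
- Affected share f: 10-40% of PDs (assumed), drawn at random.
- Survival after PD in affected subjects: exponential, median 2 or 4 months (assumed).
- 100,000 subjects per setting.

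Reading A counts every PD at its scan. B1 censors affected subjects at the PD scan. B2 counts a death within 16 weeks (two scan intervals) of that scan and otherwise censors at the scan. Kaplan-Meier results for a true median of 4 months:

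| f | A: median; 26-week PFS | B1 | B2 |
|---|---|---|---|
| 10% | 5.4 mo; 38% | 5.5; 42% | 5.4-5.5; about 41% |
| 20% | 5.4 mo; 38% | 5.6; 46-47% | 5.5-5.6; 43-44% |
| 30% | 5.4 mo; 38% | 7.2; 51% | 5.6-5.7; 45-47% |
| 40% | 5.4 mo; 38% | 7.4; 56% | 5.7-6.3; 47-51% |

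Reading A exceeds 4 months because PD is dated at the next scan. The curve falls only around scan times, so the median barely moves until it jumps one scan interval (8/4.345 = 1.8 months).

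Across settings:
- f of 10-20%, true median 2.5-4 months: the median rises 0.1-0.3 months and 26-week PFS 2-8 points.
- f of 20%, true median 6 months: B1 already jumps from 7.3 to 9.0 months.
- f of 30-40%, true median 2.5-6 months: the median rises 0.2-3.8 months and 26-week PFS 6-18 points.

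**4. Unconfirmed response.** Table 6 row 3 says a PD followed by CR or PR in the window is not a PD. SAP 9.1.2.1 says such a scan counts as the CR or PR. SAP 7.3.2.4, read as written, stops at that same PD. Confirmed mRECIST ORR is planned for Phase 2 only (7.3.2.3). For Phase 1, the only mRECIST response summary in Appendix A is Table 2.2.2, which uses the unconfirmed definition.

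**The case against.** A fair defence has five parts.

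- **Row 1 may already cover early stops.** It says the subject had ended treatment, and a subject off treatment since week 1 is still off treatment at weeks 4-6. The limit of confirmation to clinically stable subjects supports this. It stands as a possible reading, so a reader who infers that unstable subjects definitely have no mRECIST PD goes further than the text. But the heading and the introductory sentence both point the other way.
- **Other routes remain.** End of study and new anticancer therapy in the window also count the PD, and death remains an event within the Table 7 limit. This reduces the loss without removing it.
- **Late scans.** Stable subjects are meant to be rescanned at 4-6 weeks, and Protocol 7.7.1 gives a later progression date when the first PD is not confirmed. A PD scan after week 6 therefore departs from the protocol and usually delays the event.
- **Response.** Row 3 and SAP 9.1.2.1 allow the first PD in 7.3.2.4 to be read as the first PD left after Table 6. A reader might infer that Phase 1 mRECIST ORR must equal RECIST ORR. That follows only if both passages are ignored. The contradiction itself stands.
- **Size.** Censoring a share f of exponential events in continuous time multiplies the median by 1/(1 - f): 4.0 months becomes 4/0.8 = 5.0 at 20% and 4/0.6 = 6.7 at 40%. This ignores the scan schedule and every later death, so it should not be taken as the expected bias.

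**Conclusion.** The gap in Table 6 is real, and its consequence depends on the reading. Taken literally, the rule can only lengthen mRECIST PFS, DOR and duration of disease control. If row 1 includes subjects already off treatment, the shift is zero. The size cannot be derived from the documents. The ranges above rest on assumed shares, medians and survival after PD, and on affected subjects being a random draw of progressors.

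A reader might infer that PFS and DOR are biased long in general. The documents do not support that: RECIST v1.1 PFS and DOR use the first PD without confirmation (SAP 7.3.7.1, 7.3.3.1). The primary ORR and the Simon decisions that rest on it use RECIST v1.1, so they are unaffected.

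The wording of 7.3.2.4 contradicts Table 6 row 3 and SAP 9.1.2.1. It matters most in Phase 1, where it governs the only mRECIST response summary listed. Both points concern secondary or supportive mRECIST summaries and should be corrected before programming.

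**What to change.** - **Table 6.** Count the first PD as an event, dated at the first PD scan, if end of treatment, end of study, new anticancer therapy or death occurs at any time after it and before a scan showing SD, PR or CR.
- **PD scan later than 6 weeks.** State how it is handled, and reconcile this with the 6-week limit in Protocol 7.7.1. Do not set a new rule in the SAP alone.
- **SAP 7.3.2.4.** Replace *first PD* with *first PD counted as an event per Table 6*.

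The cost is SAP wording and programming, with no change to how subjects are treated or imaged. mRECIST PFS and DOR may become slightly shorter than under the literal rule.

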**Table 6: Rules for Determining PD Event Status After an Unconfirmed PD Under mRECIST v1.1**

Event Occurring After Unconfirmed PD in the Confirmation Window (4-6 weeks)	PD Event Status
Subject had end of study/end of treatment or started new anticancer therapy.	PD will be confirmed as a PD.
Subject had a confirmed PD.	PD will be confirmed as a PD.
Subject had a CR, PR, SD, or NE.	PD will not be considered as a PD and counted as corresponding CR, PR, SD, or NE for the second timepoint only.

Confirmed ORR by mRECIST v1.1 will be summarized by treatment group and tumor type for the Phase 2 response evaluable population.

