7.7. Efficacy Assessments

7.7.1. Modified RECIST v1.1 Assessment Disease

Modified RECIST will be applied by the site as the primary measure for assessment of tumor response and as a basis for Protocol guidelines related to disease status (eg, discontinuation of study therapy). As noted in Section 1.5.4.1, RECIST v1.1 has been adapted to account for the unique tumor responses seen with immunotherapy (Wolchok et al 2009).

If radiologic imaging shows progressive disease, tumor assessment should be repeated at a minimum of 4 weeks, but no later than 6 weeks later to confirm progression, with the option of continuing treatment while awaiting radiologic confirmation of progression. Table 13 provides instructions on how to proceed with treatment based on the subject's clinical status once the initial scan showing radiologic evidence of progression is observed.

Subjects may receive treatment while waiting for confirmation of progression if they are clinically stable as defined by the following criteria:

- Absence of clinically significant signs and symptoms (including worsening of laboratory values) indicating disease progression.
- No decline in ECOG performance status.
- Absence of rapid progression of disease.
- Absence of progressive tumor at critical anatomical sites (eg, cord compression) requiring urgent alternative medical intervention.

Table 13: Imaging and Treatment After First Radiologic Evidence of Progressive Disease

	Clinically Stable		Clinically Unstable	
	Tumor Imaging	Treatment	Tumor Imaging	Treatment
First radiologic evidence of progression	Repeat imaging 4-6 weeks to confirm progression	May continue study treatment at the investigator's discretion while awaiting confirmatory tumor imaging	Repeat tumor imaging 4-6 weeks to confirm progression per physician discretion only	Discontinue treatment
Repeat scan confirms progression	No additional tumor imaging required	Discontinue treatment	No additional tumor imaging required	N/A
Repeat scan shows SD, PR, or CR	Continue regularly scheduled tumor imaging assessments	Continue study treatment at the investigator's discretion	Continue regularly scheduled tumor imaging assessments	May restart study treatment if condition has improved and/or clinically stable per investigator's discretion

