##### **7.3.3.2. Duration of Response by mRECIST v1.1**

Under mRECIST v1.1, for unconfirmed objective responders, DOR is the time from the first unconfirmed overall response contributing to an unconfirmed objective response (CR or PR) to the earlier of the subject's death from any cause or first confirmed assessment of PD. Note that the criteria for the assessment of PD in DOR are the same with ORR, which are presented in Section 7.3.2.3.

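### SAP Table 6 both confirms and cancels a PD when a subject ends study or treatment, or starts new therapy, in the 4-6 week window and also has a repeat scan of CR, PR, SD or NE

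*SAP*

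**What the plan says.** SAP 7.3.2.3 asks for a repeat assessment 4 to 6 weeks after a first PD under mRECIST v1.1. It says that Table 6 "provides rules for determining whether or not the unconfirmed PD will be counted as an event in the corresponding scenario". All three rows of Table 6 refer to events in that window:

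- Row 1: "Subject had end of study/end of treatment or started new anticancer therapy". The PD is confirmed.
- Row 2: a confirmed PD. The PD is confirmed.
- Row 3: a repeat scan with any result other than PD, including one that is not evaluable. The rule then reads: "PD will not be considered as a PD and counted as corresponding CR, PR, SD, or NE for the second timepoint only".

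Other endpoints inherit this status. SAP 7.3.7.2 takes the PD component of mRECIST PFS from Table 6. SAP 7.3.3.2 does the same for duration of response: "Note that the criteria for the assessment of PD in DOR are the same with ORR, which are presented in Section 7.3.2.3". SAP 7.3.4 has a matching note for duration of disease control, and SAP 7.3.2.4 cuts unconfirmed best response at the first PD.

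Protocol Table 10, footnote m, asks for imaging around the date of discontinuation when progression has not been confirmed.

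**The concern.** The rows are not mutually exclusive. Row 1 looks only at whether the subject left study or treatment, or changed therapy. Row 3 looks only at the scan. Neither refers to the other, and no order is given in Table 6, in 7.3.2.3, in the mRECIST PFS and DOR definitions, or in the PFS censoring rules of SAP Table 7.

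Applied literally, row 1 records progression against an in-window scan that does not show it, whatever the reason for stopping. Row 3 does the reverse. The choice changes both the event status and the time in mRECIST PFS. It also changes when a response or disease control is taken to end, and whether a later response can count. In an open-label study without central imaging, an unstated rule would be chosen during programming, by people who can see the data.

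**Working it through.** No numerical figure in the plan is at issue, so the check enumerates the rules.

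**Inputs.** There are two states in the window: an event of the row 1 kind (end of study, end of treatment or new anticancer therapy), or none. There are six repeat-scan outcomes: PD, CR, PR, SD, NE or no scan. That gives 2 × 6 = 12 combinations. The PD status from every matching row is:

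| Repeat scan in window | No row 1 event | Row 1 event in window |
|---|---|---|
| PD | PD (row 2) | PD (rows 1 and 2) |
| CR | not PD (row 3) | **row 1: PD; row 3: not PD** |
| PR | not PD (row 3) | **row 1: PD; row 3: not PD** |
| SD | not PD (row 3) | **row 1: PD; row 3: not PD** |
| NE | not PD (row 3) | **row 1: PD; row 3: not PD** |
| none | no row | PD (row 1) |

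**Count.** One answer: 5 + 2 = 7. Conflict: 4. No row: 1. Total: 12.

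**What is defined.** A subject still on treatment whose repeat scan shows CR, PR or SD gets a single answer in all three cells: not PD.

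**Can the overlap occur?** Yes. Take a subject who stops for toxicity five weeks after a first PD and has the discontinuation scan of Protocol Table 10, footnote m, at that time. End of treatment and an evaluable scan then both fall in the window.

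**Worked case.** First PD at the Week 8 scan, Day 57. End of treatment and a repeat scan of SD on Day 92. The interval is 92 − 57 = 35 days, inside 28 to 42.

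- Row 1: mRECIST PFS event, dated Day 57.
- Row 3: no event at Day 57. Follow-up runs at least to the Day 92 scan, and under SAP Table 7 the subject is censored there if no later progression or death is recorded.

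**Effect on ORR.** A repeat scan of SD or NE does not make the subject a responder at that scan. A CR or PR counts towards confirmed mRECIST ORR only with a second CR or PR at least 4 weeks later. Where responder status does change, one subject is worth 1/46 = 2.2 points in the smallest full two-stage cohort of Protocol Table 19 and 1/51 = 2.0 points in the largest.

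**The case against.** The strongest reply is that the SAP already shows how it reads 7.3.2.3. SAP 9.1.2.1 counts a CR or PR found 4 to 6 weeks after an unconfirmed PD as that response, makes no exception for end of treatment, and cites 7.3.2.3. This stands in part: for CR and PR it favours row 3. But it sits in the futility section, does not mention SD or NE, and does not amend Table 6.

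A reader might take Protocol Table 13 as a planned instance of the conflict. There, clinically unstable subjects stop treatment at the first PD, may be rescanned, and if the scan shows SD, PR or CR the entry is "May restart study treatment if condition has improved and/or clinically stable". The documents do not support that reading well. The stop comes at the first PD, before week 4, so read literally row 1 is not met and row 3 alone governs. In addition, Protocol 6.2 and 6.3 tie the end of treatment to permanent discontinuation, and a subject who may restart has arguably not reached it. What remains is that the SAP does not say how a stop before week 4 is treated.

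It can also be said that row 1 is an ordinary conservative convention when there is no repeat scan. That is right, and the fix keeps it.

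**Conclusion.** The contradiction is real and narrow. It affects subjects with a row 1 event and a repeat scan of CR, PR, SD or NE in the same two-week window: 4 of the 12 combinations. SD and NE are the least resolved. The endpoints touched are mRECIST PFS, duration of response, duration of disease control, and best response and ORR, all secondary. The primary endpoint, ORR per RECIST v1.1 (SAP 7.1), does not use Table 6.

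Three stronger readings should be set aside.

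- A reader might infer that mRECIST outcomes are undefined for pseudoprogression in general. They are not: row 3 settles it for subjects still on treatment.
- A reader might infer that stopping for toxicity always becomes progression against the scan. That assumes row 1 prevails, and the SAP does not say so.
- A reader might infer a shift of a few points in mRECIST ORR. The documents give no rate for unconfirmed PD or for stopping in the window, so no estimate is possible. The number affected may be zero, and many affected subjects would not change responder status.

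This is a minor point of wording, worth settling because the two rules contradict each other.

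**What to change.** Add a precedence rule to SAP Table 6:

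1. An evaluable repeat scan in the window (CR, PR, SD or PD) decides the PD status.
2. Row 1 applies only when there is no evaluable repeat scan (none, or NE) and the subject has ended study or treatment or started new anticancer therapy.
3. The NE entry in row 3 applies only to subjects with no such event.

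This resolves all four conflicting cells. The third line is needed because otherwise end of treatment with an NE scan still meets both rows.

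Two additions complete the table: how a discontinuation before week 4 is handled, and a row for a subject still on treatment with no repeat scan in the window. Then align 7.3.2.3, Table 7 and 9.1.2.1. Table 7 uses the PD date when new therapy starts after a PD but does not say whether an unconfirmed PD qualifies.

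The cost is a few sentences in the SAP, written before the mRECIST endpoints are programmed. No new data are needed. This is an analysis rule only and has no bearing on how subjects are treated.
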